#### **10.4.2 Safety Endpoints**

Safety measurements are described in Section 5.4.1.2 and Section 9.

### **10.5 Analysis Populations**

#### **10.5.1 Efficacy Analysis Population**

The Intention-to-Treat (ITT) population will serve as the population for efficacy analyses. All randomized participants will be included in this population. Participants will be analyzed in the treatment group to which they are randomized.

#### **10.5.2 Safety Analysis Population**

The All Participants as Treated (APaT) population will be used for the analysis of safety data in this study. The APaT population consists of all randomized participants who received at least 1 dose of study treatment. Participants will be analyzed in the treatment group corresponding to the study treatment they actually receive for the analysis of safety data using the APaT population. For most participants this will be the treatment group to which they are randomized. Participants who take incorrect study treatment for the entire treatment period will be included in the treatment group corresponding to the study treatment actually receive. Any participant who receives the incorrect study treatment for 1 cycle but receives the correct treatment for all other cycles will be analyzed according to the correct treatment group and a narrative will be provided for any events that occur during the cycle for which the participant is incorrectly dosed.

At least 1 laboratory value obtained subsequent to at least 1 dose of study treatment is required for inclusion in the analysis of each specific parameter. To assess change from baseline, a baseline measurement is also required.

## 10.6 Statistical Methods

### 10.6.1 Statistical Methods for Efficacy Analyses

This section describes the statistical methods that address the primary objective.

ORR will be estimated by treatment group. 95% CI for ORR will be provided using Clopper and Pearson exact method [Clopper, C. J. and Pearson, E. S. 1934].

### 10.6.2 Statistical Methods for Safety Analyses

Safety and tolerability will be assessed by clinical review of all relevant parameters including AEs, laboratory tests, vital signs, and ECG measurements.

Individual events and the broad AE categories consisting of the proportion of participants with any AE, a drug related AE, a serious AE, an AE which is both drug-related and serious, a Grade 3-5 AE, a drug related Grade 3-5 AE, a fatal AE, dose interruption due to an AE and discontinuation due to an AE, will be summarized by counts and percentages by treatment group (Table 18).

Table 18 Analysis Strategy for Safety Endpoints

Safety Endpoint	Descriptive Statistics
Any AE	X
Any Serious AE	X
Any Grade 3-5 AE	X
Any Drug-Related AE	X
Any Serious and Drug-Related AE	X
Any Grade 3-5 and Drug-Related AE	X
Dose Interruption due to AE	X
Discontinuation due to AE	X
Death	X
Specific AEs, SOCs	X
Change from Baseline Results (lab toxicity grade)	X

Abbreviations: AE = adverse event;

### 10.6.3 Summaries of Baseline Characteristics and Demographics

The comparability of the treatment groups for each relevant characteristic will be assessed by the use of tables and/or graphs. No statistical hypothesis tests will be performed on these characteristics. The number and percentage of participants screened, randomized, and the primary reason for screening failure, and the primary reason for discontinuation will be displayed. Demographic variables (eg, age, race, etc.) and baseline characteristics will be summarized by treatment either by descriptive statistics or categorical tables.

### 10.7 Interim Analysis

No efficacy interim analysis will be conducted. One safety review by DMC is planned at ~4 months after the first participant is randomized.

### 10.8 Multiplicity

There is no hypothesis testing in this study, therefore no multiplicity adjustment is needed.

### 10.9 Sample Size and Power Calculations

The study will randomize approximately 90 participants in a 2:1:2 ratio into pembrolizumab plus epacadostat, pembrolizumab monotherapy and EXTREME arms, with 36 participants each in the pembrolizumab plus epacadostat and EXTREME arms respectively, and 18 participants in the pembrolizumab monotherapy arm. Two-sided 95% CI for ORR are shown in Table 19 and Table 20.

Table 19 Two-sided 95% CI for ORR with 36 participants

Number of Responders	ORR Estimate (%)	95% CI † of ORR (%)
11	~30	(16.4, 48.1)
13	~35	(20.8, 53.8)
14	~40	(23.1, 56.5)
16	~45	(27.9, 61.9)
18	50	(32.9, 67.1)

† Based on the two-tailed exact CI of a binomial proportion (Clopper and Pearson, 1934).

Table 20 Two-sided 95% CI for ORR with 18 participants

Number of Responders	ORR Estimate (%)	95% CI † of ORR (%)
5	~30	(9.7, 53.5)
6	~35	(13.3, 59.0)
7	~40	(17.3, 64.3)
8	~45	(21.5, 69.2)
9	50	(26.0, 74.0)

† Based on the two-tailed exact CI of a binomial proportion (Clopper and Pearson, 1934).

### 10.10 Subgroup Analyses

No subgroup analysis is needed.

### 10.11 Compliance (Medication Adherence)

Drug accountability data for study treatment will be collected during the study. Any deviation from protocol-directed administration will be reported.

### 10.12 Extent of Exposure

Extent of Exposure for a participant is defined as number of cycles in which the participant receives the study treatment infusion. Summary statistics will be provided on Extent of Exposure for APaT population.

[figure not shown]

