## 7.2 Dose Modification

The CTCAE version 4.0 must be used to grade the severity of AEs. If appropriate, the investigator may attribute each toxicity event to pembrolizumab or epacadostat or the combination in Group 1 and use a stepwise dose reduction for epacadostat according to [Table 3](#). For Group 3 (EXTREME regimen), the investigator may attribute each toxicity event to cisplatin or carboplatin, 5-FU, or cetuximab alone or in combination of 2 or 3, and

use a stepwise dose reduction according to [Table 3](#). If a dose reduction for toxicity occurs with any agent, the dose may not be re-escalated. Dose modifications are always based on the previous cycle.

Participants can have 2 levels of dose reductions per agent to epacadostat, cisplatin, carboplatin, 5-FU, and cetuximab throughout the course of the study for toxicities as described in [Table 3](#). Refer to the general instructions in [Table 4](#) for guidance regarding the re-occurrence of an AE when a participant has had their epacadostat dose reduced to dose level -2. Dose reductions of pembrolizumab are not permitted. If further toxicity occurs or the criteria for resuming treatment are not met, the participant must be discontinued from that drug and may continue to participate in the study.

For platinum toxicities refer to [Table 10](#) and [Table 11](#), 5-FU toxicities refer to [Table 12](#) and [Table 13](#), and cetuximab toxicities refer to [Table 7](#), [Table 8](#), and [Table 9](#). If a participant experiences several toxicities and there are conflicting recommendations, follow the most conservative dose adjustment recommended (dose reduction appropriate to the most severe toxicity).

For the EXTREME regimen, reduction or holding of one agent and not the other agents is appropriate if, in the opinion of the investigator, the toxicity is clearly related to one of the study treatments. If, in the opinion of the investigator, the toxicity is related to the combination of 2 agents, both drugs should be reduced or held according to recommended dose modifications. If the toxicity is related to the combination of 3 agents, all 3 agents should be reduced or held according to the recommended dose modifications. If one or more study agent(s) are held for toxicity, the schedule for restarting the agent(s) should correspond with the next treatment cycle once the toxicity has resolved according to the recommended guidelines.

Table 3 Dose Modifications for Study Treatments

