### 7.2.1 Dose Modification for Pembrolizumab and Epacadostat

Pembrolizumab plus epacadostat must be withheld for drug-related severe or life-threatening AEs. The treatment guidelines outlined in this section are intended to be applied when the investigator determines if the events are related to pembrolizumab, epacadostat, or the combination.

In all cases where pembrolizumab dosing is withheld, dosing for epacadostat should also be withheld until pembrolizumab is resumed. Participants are allowed, however, to receive pembrolizumab monotherapy if epacadostat is discontinued due to drug-related AEs.

Except in cases of emergency, it is recommended that the investigator consult with the MSD Clinical Director before temporarily interrupting therapy or permanently discontinuing any study treatment for reasons other than protocol-mandated medication hold or discontinuation.

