### 7.2.2 Dose Modifications for Cetuximab

For any delayed cetuximab treatment, do not repeat the initial dose of 400 mg/m^2. At the restart of cetuximab treatment, all subsequent infusions will be at the appropriate dose level according to [Table 7](#), [Table 8](#), and [Table 9](#). If a participant develops a toxicity that mandates interruption of therapy, the toxicity must resolve within 12 weeks from the last dose of cetuximab or the drug should be discontinued with the exception of a participant who is clinically stable and clinically benefiting from cetuximab treatment. In this case, the investigator may request that MSD allow the participant to continue to receive cetuximab.

Cetuximab therapy will not be delayed for chemotherapy-related toxicity. If chemotherapy administration is delayed, the participant may continue to receive weekly infusions of cetuximab. After resolution of toxicity, platinum and/or 5-FU may be restarted at any weekly visit when cetuximab is given (ie Day 8 or Day 15 of a cycle) as long as there are  $\geq 3$  weeks duration between consecutive chemotherapy cycles. The interval between platinum and/or 5-FU infusions will continue as Q3W from the time of the restart. If participant on the cetuximab + platinum + 5-FU arm are required to have the platinum and/or 5-FU discontinued for toxicity, the participant may continue to receive cetuximab alone. In the case of cetuximab toxicity, participant may continue on chemotherapy alone.

Table 7 Dose Modification Guidelines for Cetuximab Drug-Related Adverse Events

Category	Toxicity	Hold Cetuximab Treatment for Grade	Timing for Restarting Cetuximab Treatment	Dose for Restarting Cetuximab Treatment	Discontinue Cetuximab
Nonhematologic	Infusion reaction	2-4	See Section 7.2.2.1 and Table 8		
	Rash	3-4	See Section 7.2.2.2 and Table 9		
	All other nonhematologic toxicities 	3-4	Toxicity resolves to Grade 0-1	Reduce by 1 dose level	Toxicity does not resolve within 12 weeks of last infusion or if >2 dose level reductions exceeded
	Laboratory AE 	4	Toxicity resolves to Grade 2 or less		

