### 7.2.2.1 Infusion Reactions

Participants who experience cetuximab-related infusion reactions should have cetuximab reduced according to [Table 8](#) and continue to receive antihistamine premedication prior to administration. Once the cetuximab infusion rate has been decreased due to an allergic/hypersensitivity reaction, it should remain decreased for all subsequent infusions.

If the participant experiences a second infusion reaction at the decreased rate, cetuximab must be discontinued. If any Grade 3 or 4 infusion reaction occurs, cetuximab treatment must be discontinued immediately. Participants who experience serious infusion reactions will be discontinued from cetuximab. The participant may continue to receive chemotherapy as scheduled.

Table 8 Cetuximab Dose Modification for Infusion Reactions

NCI CTCAE Grade	Hold Treatment (Yes/No)	Dose for Restarting Treatment
1	No	Decrease the cetuximab infusion rate by 50% and monitor closely for any worsening. Note: The total infusion time for cetuximab should not exceed 4 hours.
2	Yes Stop cetuximab infusion and administer bronchodilators, oxygen, etc. as medically indicated.	Resume infusion at 50% of previous rate once allergic/hypersensitivity reaction has resolved or decreased to Grade 1 in severity, and monitor closely for any worsening.
3-4	Yes Stop the cetuximab infusion immediately and disconnect infusion tubing from the participant	Stop the cetuximab infusion immediately and disconnect infusion tubing from the participant. Administer epinephrine, bronchodilators, antihistamines, glucocorticoids, intravenous fluids, vasopressor agents, oxygen, etc., as medically indicated. Participant must discontinue treatment with cetuximab permanently.

Abbreviations: NCI CTCAE = National Cancer Institute Common Terminology Criteria for Adverse Events

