##### 2) Epacadostat Administration

Epacadostat 100 mg BID will be self-administered orally every day of each 21-day cycle. All BID doses will be taken morning and evening, approximately 12 hours apart without regard to food. If the participant vomits after taking study treatment, the participant should not take another dose. If a dose of epacadostat is missed by more than 4 hours, that dose should be skipped and the next scheduled dose should be administered at the usual time.

Participants will hold the morning dose of epacadostat for the Cycle 1 Day 1 and Cycle 2 Day 1 Visits where study treatment will be administered at the study site clinic. On days when epacadostat is administered in the clinic, participants will take epacadostat and then receive the infusion of pembrolizumab. [REDACTED]

For participants who cannot swallow tablets but can eat and/or drink, epacadostat tablets may be crushed and dissolved in water or dispersed in a medium such as applesauce, or a nutritional supplement such as Ensure® and administered orally. In the case of participants who are unable to eat or drink by mouth, the epacadostat tablet(s) may be crushed and dissolved in water and delivered to the participant through a feeding tube. Detailed information is provided in the Pharmacy Manual.

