## 10.1 Statistical Analysis Plan Summary

Key elements of the statistical analysis plan are summarized below; the comprehensive plan is provided in Sections 10.2 through 10.12.

Study Design Overview	A Phase 3 Randomized, Open-Label Clinical Study to Evaluate the Efficacy and Safety of Pembrolizumab plus Epacadostat, Pembrolizumab monotherapy and the EXTREME Regimen as First line Treatment for Recurrent or Metastatic Head and Neck Squamous Cell Carcinoma (KEYNOTE-669)
Treatment Assignment	Approximately 90 participants will be randomized 2:1:2 into 3 treatment arms, stratified by ECOG PS, HPV p16 status and prior systemic therapy (see Section 7.3.1 for details). The treatment arms are as follows: 
 
• pembrolizumab 200 mg Q3W + epacadostat;
 
• pembrolizumab 200 mg Q3W
 
• cetuximab + platinum + 5-FU (EXTREME)
 
 This study will be conducted as an open-label study.
Analysis Populations	Efficacy: Intention to Treat (ITT) Safety: All Participants as Treated (APaT)
Primary Endpoint(s)	Objective Response Rate (ORR) per RECIST 1.1 assessed by investigator determination
Statistical Methods for Key Efficacy Analyses	ORR will be estimated by treatment group with 95% CI calculated by Clopper and Pearson exact method [Clopper, C. J. and Pearson, E. S. 1934].
Statistical Methods for Key Safety Analyses	Point estimates (count and percentage) by treatment group will be provided for safety endpoints.
Interim Analyses	Efficacy 
 
• Final analysis
 
 Timing: When all randomized participants have one post-baseline imaging scan or discontinue the study. Safety: One safety review will be conducted at ~ 4 month after first participant is randomized.
Multiplicity	There will be no multiplicity adjustment.
Sample Size and Power	The sample size is approximately 90 participants with 36 participants in each of the pembrolizumab + epacadostat and EXTREME arms, and 18 participants in the pembrolizumab monotherapy arm. Section 10.9 provides the precision of the ORR estimates.

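### Section 10.12 counts exposure only as cycles with an infusion, so it never measures oral epacadostat in Group 1 and does not separate partial from full cycles in Group 3

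*Combined protocol and SAP*

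**What the plan says.** Section 10.1 presents Section 10 as complete: "the comprehensive plan is provided in Sections 10.2 through 10.12". Within it, Section 10.12 is the only place where exposure is defined: "Extent of Exposure for a participant is defined as number of cycles in which the participant receives the study treatment infusion". Summary statistics of that count are planned for the APaT population, with the same wording for every group.

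For Group 1, Table 2 lists epacadostat as a study treatment given by mouth, and Section 9.1.9.1.1 states "Epacadostat 100 mg BID will be self-administered orally every day of each 21-day cycle". Section 7.2 allows its dose to fall: "Participants can have 2 levels of dose reductions per agent to epacadostat, cisplatin, carboplatin, 5-FU, and cetuximab". Table 3 sets the epacadostat steps at 50 and then 25 mg BID. Section 7.2.1 allows it to stop alone: "Participants are allowed, however, to receive pembrolizumab monotherapy if epacadostat is discontinued due to drug-related AEs". Section 7.2.1.2 requires it to stop, while pembrolizumab may resume, after moderate or severe serotonin syndrome that other serotonergic drugs do not explain.

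For Group 3, Section 7.2.2 lets the components separate in both directions: "If chemotherapy administration is delayed, the participant may continue to receive weekly infusions of cetuximab" and "In the case of cetuximab toxicity, participant may continue on chemotherapy alone". Section 7.2.2.1 adds "If any Grade 3 or 4 infusion reaction occurs, cetuximab treatment must be discontinued immediately", with chemotherapy allowed to go on. Section 9.9.2 caps platinum and 5-FU at six cycles but sets no cycle cap on weekly cetuximab.

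**The concern.** Safety and tolerability of the three groups is the secondary objective. Readers normally set an exposure table beside the adverse event tables to see how much drug lay behind the events. The protocol does not spell out that use, but there is little other reason to plan the summary.

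The gap falls on the drug that distinguishes the arms. Sections 5.1, 5.4 and 5.4.2 say that the monotherapy arm is there to isolate what epacadostat contributes. Under Section 10.12, Groups 1 and 2 are both summarized by pembrolizumab cycles, so the table cannot show how much epacadostat Group 1 received. Appendix 4 also lets investigators attribute an event to a single agent of a regimen, and reading such attributions requires exposure by agent in Groups 1 and 3.

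**Working it through.** The plan gives no exposure figure to reproduce. The check is whether the stated rule tracks the drug received in cases that the protocol permits. All cases are hypothetical.

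**Inputs.** Epacadostat 100 mg BID is 200 mg a day, and 50 and 25 mg BID are 100 and 50 mg a day (Table 3). A cycle is 21 days. Cetuximab is given on Days 1, 8 and 15, so three infusions per cycle (Section 9.1.9.1.3). Platinum and 5-FU are given for at most six cycles (Section 9.9.2).

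**Group 1, six pembrolizumab cycles given.** This assumes that no pembrolizumab infusion is missed and that no epacadostat dose is missed apart from the change shown.

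Planned epacadostat = 6 × 21 × 200 = 25,200 mg, or 21 × 200 = 4,200 mg per cycle.

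| Epacadostat course | Taken (mg) | Share of planned | Count under 10.12 |
|---|---|---|---|
| Stopped after Cycle 1 | 1 × 4,200 = 4,200 | 17% | 6 |
| Stopped after Cycle 2 | 2 × 4,200 = 8,400 | 33% | 6 |
| Stopped after Cycle 3 | 3 × 4,200 = 12,600 | 50% | 6 |
| Stopped after Cycle 4 | 4 × 4,200 = 16,800 | 67% | 6 |
| Stopped after Cycle 5 | 5 × 4,200 = 21,000 | 83% | 6 |
| Two cycles each at 100, 50 and 25 mg BID | 21 × (2 × 200 + 2 × 100 + 2 × 50) = 14,700 | 58% | 6 |

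**Group 3, counting a cycle if any infusion is given.**

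| Course | Count | Chemotherapy cycles | Cetuximab infusions |
|---|---|---|---|
| Six full cycles, then six of cetuximab alone | 12 | 6 | 12 × 3 = 36 |
| Platinum and 5-FU stopped after Cycle 2, cetuximab to Cycle 6 | 6 | 2 | 6 × 3 = 18 |
| Cetuximab stopped for a Grade 3 reaction at the first infusion, chemotherapy to Cycle 6 | 6 | 6 | 1 (if the interrupted infusion is counted) |

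The last two participants have the same count and received very different treatment. Group 2 has one infused drug, so its count is unambiguous.

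**How often.** Section 3.2.3 reports that treatment-related events led to discontinuation in 5% of 294 participants on this combination and dose. Section 5.4 reports 20% discontinuation for adverse events with EXTREME. Applied to the planned 36 per arm, these give 0.05 × 36 = 1.8 and 0.20 × 36 = 7.2 participants. Both rates are from other studies, neither is split by agent, and neither covers holds or reductions. They indicate scale only.

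**Other planned outputs.** Section 10.11 reports deviations from the directed dosing, and a reduction or stop made under Section 7.2 is not a deviation. Table 18 counts participants with an interruption or discontinuation due to an adverse event. It has no dose-reduction row and no amount received. Section 10.6.3 displays the primary reason for discontinuation, not the amount of any agent.

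**The case against.** The strongest reply is that the infusion count is a fair proxy in Group 1. Section 7.2.1 requires epacadostat to be withheld whenever pembrolizumab is, Table 4 stops both drugs together for many severe immune events, and epacadostat is dispensed in the same 21-day cycles. This is right as far as it goes, but the link runs one way. A pembrolizumab hold carries over to epacadostat. An epacadostat reduction, or a stop of epacadostat alone, does not touch the count.

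A reader might infer that the Group 3 rule is open between any infusion and all components, so that the first Group 3 case could be reported as 12 or as 6. The documents do not support that. Section 7 defines study treatment as any of the products to be given, which makes any infusion the natural reading, and nothing suggests that all components must be given for a cycle to count. What stands is that this reading does not separate partial from full cycles.

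A reader might also infer from the worked cases that large mismatches will be common. The documents give no basis for that, and the 5% rate suggests that stops of epacadostat alone for drug-related events would be few.

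Finally, exposure is not an endpoint, nothing is tested, and the safety tables are not adjusted for exposure. All of this is true, and it limits the point to the usefulness of one descriptive summary. It is also true that summaries by agent alone would lose the one measure common to all arms, so the common count should stay.

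**Conclusion.** The point holds in limited form. Followed exactly, Section 10.12 reports full exposure for a Group 1 participant who took as little as 17% of the planned epacadostat in the cases above, because it measures pembrolizumab only. In Group 3 it gives a usable regimen-level count that hides which agents were given.

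The effect is confined to the descriptive exposure summary. The objective response rate, its exact confidence intervals and the adverse event counts and percentages are unaffected. The percentages are illustrative and rest on the dosing assumptions stated with them. The frequency of single-agent stops, holds and reductions in this trial cannot be derived from the documents. The gap is in the planned summary and not in data collection. The change is worth making because it is cheap and bears on the secondary objective; it is not a condition for the trial's validity.

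**What to change.** In Section 10.12, keep a regimen-level measure for all three arms, stated as the number of cycles with at least one study treatment infusion. Add these summaries by agent in the APaT population:

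- epacadostat: treatment duration from first to last dose, and cumulative dose taken, estimated from tablets dispensed and returned by strength;
- platinum and 5-FU: number of cycles with each;
- cetuximab and pembrolizumab: number of infusions of each;
- number of participants with a dose reduction, for epacadostat, cisplatin, carboplatin, 5-FU and cetuximab. Pembrolizumab is left out because Section 7.2 does not allow its dose to be reduced.

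The cost is one revised definition and one or two extra descriptive tables. No visit or dosing rule changes, so the revision can be made although enrollment has stopped. The schedules in Section 2 list administration by agent, Sections 7.6.1 and 7.6.3 have infusions witnessed, and Section 7.6.2 provides for epacadostat tablet counts. The drawback is that intake from tablet counts is an estimate: tablets not returned are counted as taken, so intake may be overstated. The table should say so in a footnote.
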